Summary of Pilot Study: The pilot EAW study using the ReWalk performed at the JJPVAMC trained 12 participants in the ReWalk exoskeleton for a combined total time of >1200 hours. EAW of four to six hours per week was well-tolerated by the participants. Time in the exoskeleton resulted in improved skill level. One-half of the participants reported clinically significant improvements in bladder and bowel function and reduction in pain outcome measurements. There were no study-related serious adverse events (SAEs). Skin abrasions at the points of contact with the device occurred across 9 of the 12 participants; these were reported as “study-related adverse events.” All skin abrasions were resolved with adjustments in padding and fit of the device to the participants. One participant fell due to slipping on a wet floor, but was not injured. These adverse events were consistent with those reported by others for exoskeletal-assisted walking [43, 44, 83].

II. OBJECTIVES

The short-term aims are to demonstrate in Veterans with SCI who are wheelchair users for indoor and outdoor mobility the efficacy for changes in QOL, improvements in body composition and the safety of home/community use of a powered exoskeleton for ambulation.

The long-term aims are to share the knowledge gained from this research study with the Department of Veterans Affairs (DVA) Veterans Health Administration (VHA) Spinal Cord Injury Patient Care Centers' clinical staff about the training procedures, education of and the development of guidelines for the clinical prescription of the exoskeletal-assisted walking device for home/community use in Veterans with SCI.

The study sample size is powered from preliminary data for the two primary outcomes [Mental Component Summary (MCS) of the Veterans Rand-36 (VR-36) and Spinal Cord Injury Quality of Life (SCI-QOL) assessment tool] and the major secondary outcome (total body fat mass). The secondary outcomes are exploratory and will not be used to power the study sample size.

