Sample size/power calculation for the Primary Outcome (2) SCI-QOL for Bladder, Bowel and Pain: An improvement of 10% in the sum T-score of the patient-reported outcomes from the combined SCI-QOL item banks for bladder management difficulties, bowel management difficulties and pain interference is clinically significant. As such, it is hypothesized that 42% of the Intervention group compared with 10% of the Control group will demonstrate a clinically significant change of 10% improvement from baseline to the end of the intervention phase on the sum T-score in the combined SCI-QOL item banks for bladder management difficulties, bowel management difficulties and pain interference. (Table 7).

Sample size/power calculation for the Major Secondary Outcome for Total Body Fat Mass: Patients with a new SCI can be expected to gain an average of 6.0 ± 8.9 kg of fat mass in the first 14 months after injury (manuscript in preparation from our Center). This gain in fat mass appears to continue throughout the duration of their life after SCI. As demonstrated in the preliminary data, an intervention that supports a 1.0 kg (2.2 lb.) loss of fat mass is a substantial amount of fat mass to lose in three months for a person with SCI. Very few interventions have demonstrated changes in body composition of this magnitude in the SCI population. It is expected that 35% of the Intervention group compared with 10% of the Control group will maintain total body fat mass loss during the home/community use phase of the intervention.

Assuming the proportion in the control group achieving a clinically meaningful change to be 10% (or 0.100) for all three outcome measures, and estimating the attrition rate at 15%, the sample sizes range from a low of 71 per group (95% power) for the SCI-QOL PMH outcome to a high of 79 per group (80% power) for the MCS/VR-36 group. As a note about Table 7, to adjust for multiple outcome measures, a significance level of 0.025 was used in the sample size calculations for the co-primaries (MCS/VR-36 and SCI-QOL) and also for the major secondary outcome measure (Total Body Fat Mass). Based on the sample size and power calculations in Table 7, the study will enroll a total sample size of 160 participants, 80 per group.

Table 7: Sample Size/Power Calculations			
Two group continuity corrected χ^2 test of equal proportions (odds ratio = 1) (equal n's)	MCS/VR-36	SCI-QOL (PMH)	Total Body Fat Mass
Test significance level, α	0.025	0.025	0.025

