group will have a clinically meaningful change in the outcome measures for sample size/power calculations. Ten percent is thought to be a conservative estimate as there is no reason to expect the control group to have clinically meaningful changes in quality of life measures or in total body fat mass while continuing to receive SOC for their spinal cord injury. However, as a means of verifying the control proportion of 10% (or 0.100), the proportion of participants considered successful in the control group for all three outcomes and 95% confidence intervals for the proportions will be reviewed upon the completion of the feasibility phase. Based on the extensive experience with this population it is highly unlikely that the assumed success rates in the control group (SOC) will be any higher than the assumed 10%.

At the completion of the feasibility phase, the study will be moved to a continuation phase where the remaining sites (9 remaining sites) will be activated and the remaining participants will be recruited.

D. Baseline Comparability

Baseline comparability between the treatment groups will be evaluated with respect to such variables as demographics (e.g., age, gender, and race) and baseline values of outcome measures (MCS/VR-36, SCI-QOL, total body fat mass, etc.). Chi-square and analysis of variance techniques, as appropriate, will be used to determine any differences in distribution of the variables across the treatment groups. Any variable that appears to be different between the groups ($p < 0.10$) will be considered as a potential covariate in statistical analyses.

E. General Outcome Analysis Guidelines

All statistical tests will be 2-sided. The two primary and major secondary outcome measures will be tested at a 0.025 level of significance. Because of the large number of secondary outcomes to be analyzed, all other secondary outcomes will be tested at a significance level of 0.01 to maintain control over Type I error. SAS 9.4 will be used to conduct all the statistical analyses. A variety of analytic methods will be used for the primary endpoints, secondary endpoints and other analyses.

F. Analysis of Primary and Major Secondary Outcome Measures

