As with any clinical trial, the safety of the participants will be of utmost concern. Safety will be monitored closely and data will be collected on adverse events (AEs) and serious adverse events (SAEs) throughout the course of the study. All AEs and SAEs will be systematically recorded on case report forms and coded by the CSP Clinical Research Pharmacy Coordinating Center (CSPCRPCC) at Albuquerque using the MedDRA system. The MedDRA system employs standard terminology to present adverse events and to organize them by body system. The incidence of adverse events will be summarized for each treatment group and overall by body system and MedDRA preferred term. The incidence differences between the control and intervention groups for each event will be tested using the Pearson chi-square test or Fisher’s Exact test. Table 17 illustrates how AE data may be presented for this study.

Table 17. CS #2003 Cumulative Incidence of Adverse Events by Body System and MedDRA Term

Body System and Preferred Term	SOC (n = ?)	EAW + SOC (n = ?)	All Participants (N = ?)	p-value
	n (%)	n (%)	n (%)	
All Adverse Events				
Subjects with at least one Adverse Event				
Body System 1				
Event 1				
Event 2				
Event 3				
.				
.				
.				
Body System 2				
Event 7				
Event 8				
Event 9				
Event 10				
.				
.				
.				
Body System N				
Event 14				
Event 15				
Event 16				
.				
.				
.				
Event N				

It is the responsibility of the CSPCC Study Team to provide the DMC with whatever information they feel they need to successfully monitor the study. Thus, additional tables will be added as required. In addition to the reports for the yearly meetings, the DMC will also be provided with reports between meetings at 6-month intervals.

XIV. QUALIFICATIONS

A. Site Qualifications

The Site Investigator is required to be a SCI staff physician. S/he will be responsible for the initial
 CSP #2003
 Exoskeletal Assisted Walking with Persons with SCI: Impact on Quality of Life (PEPSCI)
 Version 7.2 Protocol July 2021

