in this study. A small stipend of \$30 per visit to the SCI Centers has been included in the budget to help defray some of the expense and inconvenience of travel for participants in this study. During Screening, stipends will be given for up to 3 visits for screening/baseline evaluations (max. \$90) and up to 5 days for EAW basic training (max. \$150). At JJPVAMC, during the pilot study, it was found that participants were highly motivated to attend the 3 times weekly exoskeletal-assisted walking sessions and compliance was greater than 90%. Reimbursement for transportation and lodging may be made available to participants and companions who live more than 45 miles away from the SCI Centers. The amount will vary based on distance and will be arranged in advance with the study team.

E. Safety Considerations

Trainers will be able to identify symptoms and signs of autonomic dysreflexia (AD), such as rapid increase in blood pressure, flushing in the face, sweating above the level of injury; or symptoms of orthostatic hypotension, such as paling of the face and participant reporting lightheadedness. Study Trainers will have a policy in place at their facility in order to address these types of emergencies. These policies should include a place where the participant can be brought to a sitting position or safely laid down on the floor. Once they are in a safe position, the cause of the problem can be assessed, and appropriate steps can be taken. If there is an “error” in the ReWalk device, the Trainers will assist the participant to a sitting position using the graceful collapse feature. It will be strongly recommended that participants receiving anticoagulation therapy wear a helmet during use of the exoskeleton.

F. Foreseeable Risks

The potential risks associated with having a person with SCI dynamically load in an upright position and walk overground with a powered exoskeleton include: hypotension, low-impact fracture, falls resulting in bone fracture, muscle soreness or tear, joint damage, or other musculoskeletal injury, skin breakdown, and/or AD.

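### Safety is part of the aim to be demonstrated, but the only comparative safety analysis is a p-value for each event, with no interval, no stated level and no rule for choosing the test

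*Combined protocol and SAP*

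**What the plan says.** The short-term aims in section II cover efficacy for quality of life together with "improvements in body composition and the safety of home/community use of a powered exoskeleton for ambulation". Section XVIII.F lists the foreseeable risks of walking in the device, among them "hypotension, low-impact fracture, falls resulting in bone fracture, muscle soreness or tear, joint damage", as well as skin breakdown and autonomic dysreflexia. It gives no expected or tolerable rate for any of them.

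The comparative safety analysis is in section XIII.I, which describes reports to the Data Monitoring Committee (DMC). "The incidence of adverse events will be summarized for each treatment group and overall by body system and MedDRA preferred term". Then: "The incidence differences between the control and intervention groups for each event will be tested using the Pearson chi-square test"; the sentence goes on to allow Fisher's exact test instead. Table 17 has columns for n (%) by arm and overall, and one for the p-value.

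Section XIII.E adds that "All statistical tests will be 2-sided" and that "all other secondary outcomes will be tested at a significance level of 0.01 to maintain control over Type I error". Adverse events are not in the list of secondary outcomes, so no level is assigned to their tests. Sections XIII.F and XIII.G contain no safety analysis. The only confidence intervals mentioned in the SAP are for control-arm success proportions on the efficacy outcomes, at the end of the feasibility phase (XIII.C). The publication plan (XVII.B) says that adverse events will be reported, without saying how.

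**The concern.** A test of no difference can show that an excess of events exists. It cannot show that an excess is absent or small. The sample size was set from three efficacy outcomes (Table 7), and the events that matter most here, such as fracture, may be uncommon. A non-significant p-value is then the expected result over a wide range of true rates, including rates that a clinical service would want to know about.

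A reader deciding on home use needs to know which event rates the trial rules out. Only an interval or upper limit answers that, and none is planned.

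The open choice of test adds a second problem. With sparse data, the two permitted tests can disagree on the same table, and the level at which they would be judged is not stated.

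**Working it through.** **Inputs.** There are 80 per arm (XIII.B: "the study will enroll a total sample size of 160 participants, 80 per group"). Tests are two-sided (XIII.E) and either Pearson or Fisher (XIII.I). The level for adverse events is not stated, so 0.05 is assumed, with 0.01 (the level for other secondary outcomes) shown as an alternative. True event rates are assumed, because the documents give none.

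**The plan's own figure.** Table 7 was recomputed with the continuity-corrected two-proportion formula, control 0.10, alpha 0.025 two-sided. It gives 67, 60 and 66 per group for intervention proportions 0.333, 0.42 and 0.35 at 80%, 95% and 85% power. Dividing by 0.85 gives 67/0.85 = 78.8, 60/0.85 = 70.6 and 66/0.85 = 77.6, which round up to 79, 71 and 78. All match. The 80 per arm is therefore sound for efficacy; no safety quantity entered it.

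**Step 1: k events against none, Fisher.** With equal arms the two-sided p-value is 2 × C(80,k)/C(160,k). For k = 5 this is 2 × (80·79·78·77·76)/(160·159·158·157·156) = 2 × 0.0293 = 0.059.

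**Step 2: the same tables, uncorrected Pearson.** The statistic reduces to 160k/(160 − k) on 1 degree of freedom. For k = 3 it is 480/157 = 3.06 (p=0.080). For k = 4 it is 640/156 = 4.10 (p=0.043).

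| Intervention vs Control events | Fisher p | Pearson p (uncorrected) |
|---|---|---|
| 3 vs 0 | 0.245 | 0.080 |
| 4 vs 0 | 0.120 | 0.043 |
| 5 vs 0 | 0.059 | 0.023 |
| 6 vs 0 | 0.028 | 0.013 |
| 7 vs 0 | 0.014 | 0.007 |
| 8 vs 0 | 0.0065 | 0.004 |

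The largest non-significant count against none is therefore 3 (Pearson, 0.05), 5 (Fisher, 0.05) or 7 (Fisher, 0.01). With 5 events in total the expected count is 5/2 = 2.5 per arm, where Fisher would usually be preferred, but the plan does not say so.

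**Step 3: power.** With a control rate of 0%, power is the binomial probability that the Intervention arm reaches the first significant count: 6 for Fisher and 4 for Pearson at 0.05. The last row is by exact enumeration over both arms.

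| Assumed true rates | Fisher, 0.05 | Pearson, 0.05 |
|---|---|---|
| 3% vs 0% | 3% | 22% |
| 5% vs 0% | 21% | 57% |
| 10% vs 0% | 82% | 96% |
| 5% vs 1% | 11% | 30% |

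Fisher at 0.01 has about 5% power for 5% vs 0%.

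**Step 4: what an interval would show.** For 0/80 the two-sided 95% Clopper-Pearson upper limit is 1 − 0.025^(1/80) = 4.5%; the one-sided 95% limit is 1 − 0.05^(1/80) = 3.7%. For 5/80 (6.3%) the two-sided limits are 2.1% and 14.0%. Newcombe's 95% interval for the difference, 5/80 against 0/80, is +0.5 to +13.8 percentage points.

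**The case against.** Four points can be made for the plan.

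First, safety appears only in a general sentence on aims. The formal objectives, hypotheses and outcome lists contain no safety hypothesis, so the plan makes no non-inferiority claim and owes no margin. That stands, and no margin is asked for here. It does not remove the aim, and an aim to demonstrate safety needs an estimate with limits.

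Second, participants are protected by other means: prompt serious adverse event reporting, individual reporting of unanticipated device effects, the Site Physician's review and the DMC. Section XIII.I also allows further DMC tables. These serve monitoring during the trial. None of them pre-specifies an end-of-trial comparison.

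Third, Table 17 shows the counts, so five fractures against none would be visible and anyone could compute an interval. This is true, and it limits the harm. It also shows how little the remedy costs.

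Fourth, low power for rare events is common in trials of this size. That is a reason to report limits, not a reason to rely on p-values.

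Two stronger readings are tempting and should not be drawn. A reader might infer that the plan would declare no difference, or safety, from a non-significant test; no passage says so. A reader might also take five against none as the general threshold; it holds only for Fisher at two-sided 0.05, and under uncorrected Pearson at 0.05 the same result is significant. Nor is it apt to recompute the figures on the 68 expected completers per arm, because section XI.E collects adverse events from consent until completion or early termination, so drop-outs contribute.

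**Conclusion.** The point holds as a gap between a stated aim and the analysis that serves it. The plan's only comparative inference on safety is a per-event p-value with no level and no rule for choosing the test. With no control events, that leaves the largest non-significant count anywhere from 3 to 7 of 80. At an assumed 5% against 0%, the test misses the difference 79% of the time by Fisher and 43% by uncorrected Pearson at 0.05, so non-significance is weak evidence either way.

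The size depends on the assumed rates: at 10% against 0%, both tests at 0.05 have power above 80%. The absence of any planned safety interval does not depend on them. The sample size, the data collection and the efficacy analyses are unaffected. This is an inexpensive improvement that should be made; it does not show that the trial is unsafe or its design unsound.

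**What to change.** In section XIII.I, for serious adverse events and for the risks listed in section XVIII.F, add to Table 17, among all randomized participants:

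- the exact two-sided 95% Clopper-Pearson limits for the Intervention incidence;
- a 95% confidence interval for the risk difference, with the method named. The method matters: for 5 against 0, Newcombe's interval excludes zero although Fisher's p is 0.059.

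Specify Fisher's exact test for sparse events and state its significance level. State that safety conclusions rest on the interval limits and that a non-significant p-value is not evidence of no added risk. State also what is attainable: zero events in 80 gives a two-sided upper limit of 4.5% (3.7% if one-sided), and 5 in 80 gives 2.1% to 14.0%. Say that the same table will be used in the final report, since at present it is described only for the DMC.

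The cost is some SAP wording and a few extra columns, from data already collected. The downside is a more modest safety statement for rare events.

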Data collection which contains any protected health information (PHI) such as informed consent forms, Health Insurance Portability and Accountability Act (HIPAA) forms, and contact information will be stored within each individual site and will remain either in locked cabinets or electronically behind the VA firewall in a password-protected file. Only approved study personnel will be permitted access to view study related folders. In addition, access to the study folders stored on the VA network will be restricted to personnel listed on this study. This will further limit access to files stored on the VA network that contain PHI and outcome data related to this study.

SharePoint will be utilized within this study as it has been considered an approved collaboration environment and access to the SharePoint site can be restricted by the study team as needed.

SharePoint will be utilized as an intranet portal to maintain documents, manage files and other collaborative efforts securely. All data will be sent to the Coordinating Center at Perry Point using DataFax which is a system to send case report forms using a fax machine to Perry Point which will maintain the data repository for all sites. To ensure that all questions are answered on the QOL outcome assessments (VR-36, SCI-QOL, Global Impression of Change Scale (Participant- and Companion-rated), PROMIS Sleep Disturbance, SCI-FI, and bowel function surveys), the site's study staff will conduct in-person or telephone interviews. Testing and survey procedures will be conducted in private rooms and training will be performed in rooms and hallways of the VA SCI Services, on the medical center grounds when weather conditions permit, at Community Based Outpatient Centers (CBOCs) under the same FWA number as the VA facility conducting the research, and/or in the participant's home or community.

XVI. DATA MANAGEMENT AND DATA SECURITY PLANS

Most data collection will be non-sensitive data that will be coded using a subject number that will link the data to a specific subject. Data collection may also take place through secure messaging using My HealtheVet. The code to the subject number will be stored in a separate secure location within the VA Network at each site. Access to sensitive data will be restricted to authorized users; access will be related to VA-approved research, data users and custodians. VA and non-VA staff will be aware that they must immediately report theft or loss of VA sensitive data or media containing VA sensitive data to the site VA Information Security Officer (ISO). Electronic VA sensitive data will be collected, used and stored on VA computers on the VA network (behind the VA firewall), on restricted access drives, and in password protected files. Hard copies of VA sensitive data will be collected and used, and stored in locked cabinets in locked rooms. Any code linking identities to data will be stored separately from the data, electronically behind the VA firewall or hard copy in a locked cabinet in a locked room. Special access will be granted to study-related data to the sponsor and regulatory boards upon request. This will include representatives of the Food and Drug Administration (FDA), the Central Institutional Review Board (CIRB), Office of Research Oversight (ORO), and compliance officers, etc. Written documentation of any review of study related files will be required. This documentation will be stored with the study related paperwork. All subjects that are enrolled in the CS #2003 study will be informed of any potential review by these regulating bodies during the consent process.

Training for data collection and management will be conducted for all sites prior to initiating the study in order to ensure that the data is collected in the same manner and all study staff understand

the source documents and case report forms. Data from the sites will be sent to the Coordinating Center, [name]. All hard copies of case report forms collected will be stored within locked cabinets at the sites. Electronic data will be stored on servers protected by the VA firewall. This study will utilize SharePoint as a method of maintaining documents and collaborating across the other VA sites. Restricted and selective access can be granted administratively to the SharePoint environment in order to prevent unauthorized access.

QOL outcome assessments (VR-36, SCI-QOL, Global Impression of Change Scale (Participant- and Companion-rated), PROMIS Sleep Disturbance, SCI-FI, and bowel function surveys) will be completed by each participant during an in-person or phone interview by a member of the study site staff. The interviewer will record the answers, making sure that all questions are answered. This data will be sent to the CSPCC via a Datafax system.

XVII. PLANS FOR DISSEMINATION OF STUDY RESULTS

A. Publication of Research Results

It is the policy of the Cooperative Studies Program not to reveal outcome data to Site Investigators until the data collection period of the study is complete. This policy is meant to prevent possible biases that might affect data collection. Members of the DMC will be reviewing outcome results to ensure that the study will be terminated early if a treatment is identified as prohibitively dangerous or if a definitive answer is reached prior to the scheduled study termination date.

All presentations and publications resulting from this study will follow CSP policy as specified by the CSP guidelines. The presentation or publication of any or all data collected by Site Investigators on patients entered into a Department of Veterans Affairs Cooperative Study is under the direct control of the study's Executive Committee. No individual Site Investigator has the right to use the study's data to perform analyses or interpretations, or to make public presentations or seek publication of any or all of the data without specific approval of the Executive Committee.

The Executive Committee has the authority to establish any number of publication committees, which usually will comprise of subgroups of Site Investigators and some members of the Executive Committee, for the purpose of producing manuscripts for presentation and publication. Any presentation or publication related to this study should be circulated to the Executive Committee for review, comments and suggestions at least four weeks prior to submission of the manuscript to

the presenting or publishing body.

All publications must give proper recognition to the funding source and should list all study participating site personnel (not necessarily as authors of the manuscript). If an investigator's major salary support and/or commitment is from the VA, it is obligatory that the investigator lists the VA as his/her primary institutional affiliation. Submission of manuscripts or abstracts must follow the usual VA policy; ideally, a subtitle states, "A Department of Veterans Affairs Cooperative Study." The CSP also requires that every manuscript be reviewed and approved by the CSPCC Director prior to submission as a final quality control step. Mechanisms for appeal by an investigator will follow procedures defined by the VA Office of Research and Development. Participation in a Department of Veterans Affairs Cooperative Studies Program clinical trial is voluntary. Any investigator who cannot accept these operational guidelines regarding publication policy should not volunteer to participate in the study.

B. Planned Publications

The Executive Committee, led by the study Chair, [name], on behalf of the study group, will prepare the primary outcome manuscript and investigators with special interest will prepare the secondary outcome manuscripts in each of these areas, as to be determined by the Executive Committee. The Executive Committee will consider additional ideas for sub-study manuscripts from members participating in the study. Sub-study activities (within the scope of this original protocol) may be authorized by the Executive Committee to address other important research questions raised.

Primary publication: Upon completion of the study, a manuscript will be prepared that focuses on the primary outcome, i.e. the proportion of subjects demonstrating a clinically significant change in MCS/VR-36 and the patient-reported outcomes for SCI-QOL bladder management difficulties, bowel management difficulties and pain interference, as compared between the Intervention and Control groups. This proportion of participants who achieved the major secondary outcome for total body fat mass changes will also be reported in the primary manuscript. Any adverse events will be reported as well.

Other publications: Upon completion of the study and the acceptance of the primary manuscript for publication, the secondary outcomes will be analyzed for the PROMIS sleep disturbance, bowel function survey, the remaining items in the SCI-QOL that were not included in the primary

outcomes, the physical function domains from the SCI-FI, and lipid profile results. The amount of time spent in the device and location of use will be reported in conjunction with any of the above manuscripts.

XVIII. HUMAN SUBJECTS PROTECTION CONSIDERATIONS

A. Recruitment of Participants and Special Considerations

The targeted study population to be studied is Veterans or military members with SCI (>6 months) who are non-ambulatory and a primary wheelchair user for mobility. The Site Investigator is required to be a SCI staff physician. S/he will be responsible for the initial contact with any potential participants. Once a potential participant expresses interest and gives verbal permission to learn more, additional study team members will assist the Site Investigator with the informed consent and eligibility screening process. There are no race, ethnicity or gender limitations for enrollment. The age range is limited to who are at least 18 years of age. There is no upper age limit because if someone passes all the inclusion and exclusion criteria, being of an older age, but in good health should not be exclusionary in of itself. Special classes of subjects such as pregnant women, prisoners, institutionalized individuals, or other populations that may be considered vulnerable will be excluded from this study with the exception of economically and educationally disadvantaged persons. There are Veterans and military members who are economically, educationally or socially disadvantaged individuals and they will be given the opportunity to participate in this research project. These disadvantaged persons will be given the same treatment as individuals who are not considered to be vulnerable.

B. Inclusion of Women and Minorities in Study

Consistent with the Belmont Report, “Ethical Principles and Guidelines for the Protection of Human Subjects,” and Congressional legislation, eligible women and minorities will be included in this study.

C. Description of the Consenting Process

Consent will be obtained prior to study enrollment by the Site Investigators or a member of the study research team. Study team members will be trained to obtain consent. They will be responsible for explaining the proposed clinical trial and answering questions before obtaining

informed consent. The consent will be explained in its entirety by the study team. The terms of the consent form will be explained prior to obtaining the individual's signature. Individuals will be given the opportunity to take the consent home for review with family members (if they so choose), to think about it overnight, and to ask questions prior to signing the consent form. Participants will be asked to explain back to the study team member what they believe the study entails, thus giving the opportunity for the study team member to correct any misunderstandings or add further detail. Potential participants will be informed of their right to ask questions at any time during the trial and/or to withdraw at any time. The potential participants will be informed that choosing to not participate or to withdraw will not infringe on any of their regular VA benefits or medical care.

The timing of the consent process will take place prior to any screening assessments. The location of the consent process will primarily be in the site's area where the research will be conducted, but is not limited to these areas. Additional locations where the consent process could take place include a physician's office, the investigator's offices, and/or designated rooms where privacy can be maintained (to include Community Based Outpatient Centers (CBOCs) under the same FWA number as the VA facility conducting the research). Additional locations could include the participant's home or community space where privacy can be maintained.

During the consent process, the participant's privacy will be maintained by using a private room. Participants who wish to have a family member or a friend in attendance during the consent process may do so. Ample time for decision making will be provided and the potential participant will be allowed and encouraged to discuss the proposed clinical trial with anyone before making a decision.

There will not be a plan for the consent of the individual's Legally Authorized Representative because an inability to sign consent is exclusionary to this clinical trial.

*Consenting of the companions may be obtained at the time the participant consents or during the Screening Phase for the enrolled participants. Consenting of the companions may take place in person or assent may be obtained over the phone.

D. Participant Compensation

A potential barrier to recruitment is the travel and time commitment for persons with SCI to enroll

in this study. A small stipend of \$30 per visit to the SCI Centers has been included in the budget to help defray some of the expense and inconvenience of travel for participants in this study. During Screening, stipends will be given for up to 3 visits for screening/baseline evaluations (max. \$90) and up to 5 days for EAW basic training (max. \$150). At JJPVAMC, during the pilot study, it was found that participants were highly motivated to attend the 3 times weekly exoskeletal-assisted walking sessions and compliance was greater than 90%. Reimbursement for transportation and lodging may be made available to participants and companions who live more than 45 miles away from the SCI Centers. The amount will vary based on distance and will be arranged in advance with the study team.

E. Safety Considerations

Trainers will be able to identify symptoms and signs of autonomic dysreflexia (AD), such as rapid increase in blood pressure, flushing in the face, sweating above the level of injury; or symptoms of orthostatic hypotension, such as paling of the face and participant reporting lightheadedness. Study Trainers will have a policy in place at their facility in order to address these types of emergencies. These policies should include a place where the participant can be brought to a sitting position or safely laid down on the floor. Once they are in a safe position, the cause of the problem can be assessed, and appropriate steps can be taken. If there is an “error” in the ReWalk device, the Trainers will assist the participant to a sitting position using the graceful collapse feature. It will be strongly recommended that participants receiving anticoagulation therapy wear a helmet during use of the exoskeleton.

F. Foreseeable Risks

The potential risks associated with having a person with SCI dynamically load in an upright position and walk overground with a powered exoskeleton include: hypotension, low-impact fracture, falls resulting in bone fracture, muscle soreness or tear, joint damage, or other musculoskeletal injury, skin breakdown, and/or AD.

To date the investigative staff at the JJPVAMC has trained 12 participants to use the ReWalk system. In these initial 12 participants, there were no study related SAEs. One participant fell as a result of undetected water on the floor, but was not injured from the fall. There were minor skin abrasions (reported as study-related adverse events), which were resolved with additional padding and alterations in the fitting of the device. The group who initially studied the ReWalk at Moss

Rehabilitation Hospital, Philadelphia, PA reported their adverse events [43]. Esquenazi et. al., reported the following adverse reactions during his phase 1 clinical trial performed at Moss Rehabilitation Hospital, Philadelphia, PA: “(1) skin abrasions in areas of contact with the device, (2) lightheadedness, and (3) edema of the lower limbs [43, 83]. They were all managed by the appropriate use of (1) foam and padding, (2) caffeinated beverage intake and adjustment of blood pressure medication, (3) elastic stockings and rest, respectively. There were no detrimental changes in vital signs or complaints of lightheadedness with prolonged standing.” Additional hazards to walking overground using a robotic exoskeleton include the risk of equipment malfunction, battery dying, or any unknown or unpredictable problem.

There are also some risks associated with the measurements obtained by the dual x-ray absorptiometry (DXA) scanner and the bilateral calcaneus x-rays. These medical diagnostic devices emit small amounts of radiation, approximately $8\mu\text{Sv}$ (DXA) and $2\mu\text{Sv}$ (bilateral x-rays). This amount of radiation is similar to normal background radiation amounts from radon, food, water, and cosmic radiation. There are risks associated with phlebotomy which include pain, swelling, bruising or skin irritation at the site of the venous puncture and rarely, syncope in persons who are susceptible to a vasovagal response. There are risks associated with anticoagulation therapy if a participant were to fall and hit their head. It will be strongly recommended that participants receiving anticoagulation therapy wear a helmet during use of the exoskeleton.

G. Risk Management and Emergency Response

All potential participants will be examined and their medical charts will be reviewed by the study team physician (who is also a member of the study site’s medical center staff) before being cleared for participation. Study personnel will be in attendance at all times while a participant is using the exoskeleton and while all testing is being performed. Blood pressure and heart rate will be monitored before, during, and after the training sessions, primarily to identify changes in blood pressure. The study staff will query the participants throughout each session for early signs or symptoms of hypotension such as feeling light headed or queasiness. During the sessions, persons with a fall in blood pressure from their pre-session seated BP of $>20/10$ mmHg will be seated or brought to a supine position. The staff involved with this study will be trained to look for signs and symptoms of AD. Most persons with SCI are also knowledgeable about AD, but all participants will also be made aware of these signs and symptoms of AD. The legs where the straps are fastened will be examined for skin breakdown during (as needed) and after training sessions to ensure that there are no areas that may be abrading. If evidence of skin redness,

irritation or breakdown exists, alternate placements for straps and/or padding will be used to protect the area. Participants who have continued breakdown will be temporarily discontinued. Participants will be checked after each session for signs of edema. If edema is present, participants will be instructed to elevate their feet, use compression socks for the next session, and/or reduce the upright time or training frequency. If edema persists more than one day, the participant will be referred to the Site Physician. Training sessions will be discontinued if need be.

